## 7.3 Model Development

### 7.3.1 Data preparation and missing data for cohort 1

There will be an initial exploration to examine quantity of candidate variables within the dataset and the parameters within each one. This exploration will also identify missing data, and highlight any variables that may need cleaning or preparing in anticipation of model development. The outcome variable will be created using the variables derived from the ED data. Once created, the ED variables will be removed from the dataset. This completes the data preparation stage.

Any missing data will be assessed for randomness using statistical methods such as Little's Missing Completely at Random Test. If there is a small (<2%) of random data missing, then complete case deletion of the missing data will be considered. Alternatively, any arbitrary missing data will be handled with multiple imputations. Any monotonic pattern of missing data will be approached after further consultation with a statistician to prevent systematic bias entering into the models.

Following on from this, the cohort 1 sample will be compared to the unlinked data to assess for screening bias. Once this is complete, the unlinked data will be destroyed.

Predictive models will be developed and applied to the data independently. There will be a preference to use the whole dataset to derive each model and then use resampling techniques such as bootstrapping to measure optimism and recalibrate, (as opposed to sample splitting). For models which do require a training set and test set, this split will be done non-randomly, with the test data being unlabelled.

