### 3.2 Secondary research questions

What is the simulated transportability of the model derived from the primary outcome?

Which classification model is most accurate at predicting an avoidable attendance at the ED in adults?

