#### 3.2.2 Secondary outcome measure

Avoidable attendance at ED as defined by O’Keeffe et al. (2018)

Comparative accuracy in prediction, misclassification rate, imprecision and inaccuracy.

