### 7.4.3 Internal validation

For the logistic regression model this can be performed using bootstrapping of cohort 1 to measure the optimism and then apply the shrinkage factor to the beta coefficients. For methods such as random forest modelling, they would need alternative methods such as cross-validation. Once all models have been internally validated, they will be applied to cohort 2.

There will be a sub-group analysis using non-random splitting of cohort 1 according to individual variables. The performance in the sub-groups can then be plotted in a graphical way such as a calibration plot or ROC curve. This will enable the identification of groups of patients the model is more vulnerable/ robust towards.

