### 7.4.4 Model selection

Once all adjusted models have been created and tested on cohort 2, there will be a comparative analysis of model performance using the same methods described above. The CI will then present the models to a small expert panel for independent confirmation. This panel will be a combination of clinicians and statisticians.

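### The validation route depends on the model type and no common labelled comparison is fixed, so a model scored on a non-random split could be ranked on its scheme rather than its merit

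*Protocol*

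**What the plan says.** The second secondary question (Protocol 3.2) is "Which classification model is most accurate at predicting an avoidable attendance at the ED in adults". Section 3.2.2 sets its outcome as "Comparative accuracy in prediction, misclassification rate, imprecision and inaccuracy", and section 4 ends phase 2 when the most accurate model has been chosen.

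The routes to a performance estimate are these:

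- **General preference (7.3.1):** "There will be a preference to use the whole dataset to derive each model and then use resampling techniques such as bootstrapping".
- **Exception (7.3.1):** "For models which do require a training set and test set, this split will be done non-randomly, with the test data being unlabelled". Neither the basis of the split nor the models concerned are named.
- **Logistic regression (7.4.3):** "For the logistic regression model this can be performed using bootstrapping of cohort 1 to measure the optimism", followed by shrinkage of the coefficients.
- **Other methods (7.4.3):** "For methods such as random forest modelling, they would need alternative methods such as cross-validation".

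The metrics are common to all models (7.3.3): sensitivity, specificity, PPV, NPV, C-statistic and calibration. At derivation they describe apparent performance only. On the comparison itself, 7.4.4 says: "Once all adjusted models have been created and tested on cohort 2, there will be a comparative analysis of model performance". Section 7.4.2 says that cohort 2 is unlinked and that no outcome will be created for it.

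**The concern.** A head-to-head comparison needs the models to differ and everything else to stay the same. Here the estimation scheme may differ along with the model. Bootstrap correction and cross-validation both use the whole of cohort 1 and estimate performance in that population. A model on a non-random split is fitted to fewer records and scored on a subset that may have a different case mix. The C-statistic depends on case mix, and PPV and NPV depend on prevalence as well, so such a model can rise or fall in the ranking for reasons unrelated to its quality.

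No later step repairs this. Cohort 2 receives every validated model but has no outcome. Apparent performance on the whole of cohort 1 is common to the models derived on it, but it flatters flexible models. The fair comparison therefore has to come from internal validation in cohort 1, which is where the routes diverge.

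The word 'unlabelled' adds a second problem: if the test records truly carried no outcome, none of the metrics in 7.3.3 could be computed on them. What is at stake is which model is selected.

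**Working it through.** **1. Scale, from Protocol 7.2.** These figures only set the scale for what follows.

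- Inputs: 520 parameters, 50 events per variable, 9% prevalence, 80% linkage, 7.7% incomplete outcome.
- Events required: 520 × 50 = 26,000. Records: 26,000 / 0.09 = 288,889.
- Plan's inflated figure: 288,889 × (1 + 0.20 + 0.077) = 368,911, which reproduces the stated number.
- Records left after both losses: 368,911 × 0.80 × 0.923 = 272,404.
- Events: 272,404 × 0.09 = 24,516, or 24,516 / 520 = about 47 per parameter. Non-events: 247,888.

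**2. Sampling precision of a C-statistic (Hanley-McNeil).** C = 0.80 is an assumption; the protocol gives no expected value.

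- A = C/(2 − C) = 0.80/1.20 = 0.667. B = 2C²/(1 + C) = 1.28/1.80 = 0.711.
- SE² = [C(1 − C) + (24,516 − 1)(A − C²) + (247,888 − 1)(B − C²)] / (24,516 × 247,888), so SE = about 0.0017. The 95% half-width is 1.96 × 0.0017 = about 0.003.
- With C = 0.70 instead, A = 0.538 and B = 0.576, and SE = about 0.0019.
- On a 30% test set with the same prevalence and C = 0.80, SE = about 0.0017/√0.30 = 0.003.

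This is sampling error only. It says nothing about how large a scheme effect would be.

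**3. Illustrative size of a scheme effect.** A logistic model was simulated with 60 predictors, 31,500 records, prevalence about 9% and about 45 events per predictor, close to the planned ratio. There were 6 repeats. The effect sizes are assumed, including one strong predictor. The same model type was scored under each scheme, so differences come from the scheme alone.

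| Scheme | Mean C-statistic | Difference from bootstrap |
|---|---|---|
| Apparent | 0.7486 | +0.0055 |
| Bootstrap-corrected | 0.7431 | – |
| 10-fold cross-validation | 0.7416 | −0.0015 |
| 70/30 split by record order | 0.7411 | −0.0020 |
| Split, test set = bottom 30% of strong predictor | 0.7017 | −0.0414 |
| Split, test set = top 30% of strong predictor | 0.6961 | −0.0470 |

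The record-order split stands in for a split by time with no drift. Bootstrap, cross-validation and that split agree to within 0.002. Splitting on a strong predictor moves the estimate by about 0.04 to 0.05. No random forest was simulated.

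**4. Is the outcome available in a cohort 1 test set?** Section 7.3.1 says: "The outcome variable will be created using the variables derived from the ED data". This belongs to data preparation, before any split. Section 7.3.3 then requires accuracy statistics for each model. Outcomes should therefore exist for test records with complete ED data, and 'unlabelled' most plausibly means hidden from the model until scoring. The protocol does not say so.

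**The case against.** The best defence is that the plan prefers resampling of the whole dataset and treats splitting as an exception. The two model families it names, logistic regression and random forest, both get resampling of labelled cohort 1 data, and no named model is assigned to the split. Much of the wording is permissive, so a single scheme is not ruled out. The metrics are common, and selection also weighs feasibility (3.2.1) and an expert panel's view (7.4.4). Fold structure, nested tuning and the source of subgroup predictions can be left to an SAP.

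Most of this stands, and it rules out three stronger readings that a reader might infer:

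- **That every model type has its own validation method, so the accuracy question cannot be answered fairly.** The text does not go that far. Bootstrap and cross-validation on cohort 1 estimate much the same thing, and cohort 1 outcomes would permit one scheme for all.
- **That split-based models will have no performance estimate.** This needs the literal sense of 'unlabelled', which fits poorly with an outcome built before the split.
- **That a standard error of about 0.0017 proves the scheme effect would distort the ranking.** It shows precision, not the size of the effect. The gap of 0.04 to 0.05 needs a split on a strong predictor, which the protocol does not specify.

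What the defence does not remove is that the protocol itself states a model-dependent rule, including a non-random split for some models only. It then compares the models without requiring common held-out records with known outcomes. That is a rule in the text, not merely detail awaiting an SAP.

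**Conclusion.** The point holds in limited form. As written, the model ranking is not protected from an effect of the validation scheme, and applying the models to cohort 2 cannot supply the missing comparison. For logistic regression against random forest, a bootstrap versus cross-validation mismatch is a small worry: about 0.0015 in C-statistic in the simulation, which compared the schemes on logistic models only. For any model sent down the split route, the effect could range from negligible to about 0.04 to 0.05, depending on a split basis that the protocol does not give. These sizes rest on assumed effects and are illustrative.

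'Unlabelled' is an ambiguity to resolve, not proof that a test set cannot be scored. Because the comparison decides which model is selected, the wording should be settled before models are fitted.

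**What to change.** Amend 7.3.1, 7.4.3 and 7.4.4 as follows.

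1. Base the model comparison on one resampling scheme in cohort 1, with the same folds or the same bootstrap resamples for every model. Repeat tuning and variable selection inside each training part.
2. Score every model on the same held-out records with known outcomes, and report paired differences with intervals.
3. Replace 'unlabelled' with a statement that test outcomes are masked during fitting and prediction and then used for scoring.
4. If a non-random split is wanted, state its basis and apply it to all models as an added test, not as the only test for some.
5. State that cohort 2 does not contribute to the accuracy comparison.

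Patients may have up to four contacts under the exclusions in 6.2, so folds grouped by person would be preferable. Section 8.2.1, however, creates the unique ID per care record and leaves no other identifier after linkage. Group folds by person only if the extract carries a pseudonymous person key.

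The cost is wording and more computing time. The common scheme needs no new data; a person key, if wanted, would mean a changed extract.

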### 7.3.2 Predictors

There will be no a priori candidate variables selected. Instead, all clinical variables collected during the paramedic patient assessment and/or treatment will be included in the initial development. Lower Super Output Area (LSOA) will be recoded into an Index of Multiple Deprivation (IMD) score which will be used as a predictor. It is anticipated there will be twenty three variables across three domains as described by table 1. Penalisation will be used in logistic regression to eliminate variables which have little or no effect on the outcome. Such methods include Ridged, LASSO and Elastic Net.

Table 1: Example of possible candidate predictors

Physical factors	Social factors	Interventional factors
Age	Location	Airway
cABC (initial assessment)	Dementia	Drug administration
Working impression	Communication	Cannulation
Allergies	DOLS	Resuscitation
Medication	Mental capacity	Extrication
Primary NEWS	Moving and handling aids	Clinical procedures
Subsequent NEWS	Mobility	Patients advice
FAST	IMD	

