# ix. Study flow chart

## DATA FLOW DIAGRAM OF DATASET PREPARATION AND LINKAGE

## DATA FLOW DIAGRAM OF DATASET USAGE

# 1 Background

## *The demand problem*

Demand for the urgent and emergency care system is increasing (~5.2% annually). 10.7 million calls were transferred to the ambulance service with 6.6 million receiving a face-to-face attendance. The vast majority of these calls were urgent and not emergencies. This demand is also mirrored in ED, which results in delays when the ambulance service is handing the patient over. In a 3 month winter period in 2017/18 in England, there were 41,879 patient episodes where an ambulance took over an hour to handover to the ED. There is international evidence from the USA, Canada, UK and Australia showing ambulance ramping can be both a consequence and a cause of ED crowding. Queuing ambulances means less resources are available to respond to 999 calls, which has a damaging effect on patient care and ambulance service performance. Furthermore, the accuracy in the decision to convey a patient to the ED is not always accurate. A 2018 study found that up to 16.9% of ambulance conveyances to the ED were potentially avoidable. This study used a process-based validated definition of avoidable, which is being used in this project as the primary outcome measure.

More evidence is required in identifying patients who are likely to have an avoidable conveyance to the ED, whilst they are still with the ambulance service on-scene.

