## 8 Data Management

### 8.1 Data collection tools and source document identification

Yorkshire Ambulance Service has an ePCR system in place across the whole region. This is a compulsory system for paramedics to create and complete individual care records for each patient which begins at arrival on scene, and is completed once the patient is handed over. This document forms the source document for each patient that will be eligible in this project. The sample size in section 10.2 is in effect calculating the number of source documentation required for model derivation and validation.

Within each source document is the variables required to derive and validate the model. An example of the variables within can be seen in table 1 (above). The variables are mainly categorical and presented as drop down lists. The other type of variable captured is continuous such as age. The clinician is expected to fully complete each record however not all fields are compulsory capture.

This is a retrospective study and as such, there will be no attempt to maximise completeness of data. The sample size has been inflated to account for expected source document attrition at the point of data retrieval. The methodology has accounted for the handling of missing data.

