# 11 Dissemination Policy

## 11.1 Research outputs

### 11.1.1 Anticipated research products

- A toolkit that can support clinicians in deciding the likelihood of an avoidable attendance before transporting the patient. This can be built into an electronic patient care record and used to support clinical assessment and decision making. Outputs will be disseminated through peer review publications, presentation at relevant conferences.
- A Systematic review of risk prediction modelling in the urgent and emergency care system.
- New knowledge on what clinical assessment variables contribute most to risk stratifying patient's on scene.
- New knowledge on using risk prediction modelling in the prehospital setting and the potential feasibility of more complicated models such as machine learning in assisting clinical decision making.
- New knowledge on how to manage patient expectations on-scene.
- New knowledge on how to influence/change a clinician's decision on-scene by presenting them with patient risk.
- Two anonymous linked datasets of clinical care prehospital and in hospital data that other projects can use for further analysis.
- Further research plans for refining the tool, implementation and testing under real world conditions such as a randomised controlled trial.

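### No prediction time is fixed, so up to 8 of the 23 example predictors can hold values recorded after the transport decision that the tool is meant to inform

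*Protocol*

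**What the plan says.** Section 7.3.2 states "There will be no a priori candidate variables selected" and instead that "all clinical variables collected during the paramedic patient assessment and/or treatment will be included in the initial development". It adds: "It is anticipated there will be twenty three variables across three domains as described by table 1". Table 1 is titled "Example of possible candidate predictors". It lists "Subsequent NEWS" separately from Primary NEWS, and it has an interventional column of seven items: airway, drug administration, cannulation, resuscitation, extrication, clinical procedures and patients advice.

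Section 8.1 says that the electronic patient care record (ePCR) "begins at arrival on scene, and is completed once the patient is handed over". Under section 6.1, the cohort 1 ambulance records are those of patients transported, handed over and booked in at an ED. Cohort 2 is patients discharged on scene.

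The intended use is stated twice. Section 1 (The demand problem) asks for evidence on "identifying patients who are likely to have an avoidable conveyance to the ED, whilst they are still with the ambulance service on-scene". Section 11.1.1 names as the first product "A toolkit that can support clinicians in deciding the likelihood of an avoidable attendance before transporting the patient".

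**The concern.** A prediction model should be built only from what is known when the prediction is made. Here that moment is on scene, before the decision to convey. The derivation records run past it for every patient, and the predictor rule admits whatever the record contains at closure.

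A repeat NEWS taken on the journey, or a treatment given because the crew had already decided to convey, would carry information that the clinician using the tool does not yet have. Three things would be at stake:

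- **Performance.** Discrimination and calibration reported for the model might not apply at the point of use.
- **Model choice.** Section 7.4.4 selects among models on comparative performance, so a model that makes better use of late entries could be preferred for that reason.
- **Application to cohort 2.** Those patients had no journey, so predicted risks could shift for reasons unrelated to need.

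**Working it through.** **1. The protocol's own count.** The columns of Table 1 hold 8 physical, 8 social and 7 interventional items: 8 + 8 + 7 = 23. This agrees with the figure in section 7.3.2.

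**2. Items that can hold post-decision values.** Subsequent NEWS (1) plus the interventional column (7) gives 8, and 8/23 = 35%. A narrower reading that counts only Subsequent NEWS and extrication gives 2, and 2/23 = 9%. The protocol gives no entry times, so it does not settle where the true number lies; even the two items of the narrower reading are placed after the decision by inference. The count of 8 also treats the other 15 items as known on scene.

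**3. The statements side by side.**

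| Element | What the protocol fixes | Where |
|---|---|---|
| Moment of use | On scene, before transport | 1; 11.1.1 |
| Span of the record | Arrival on scene to handover | 8.1 |
| Derivation cohort | All conveyed and handed over | 6.1 |
| Predictor rule | All assessment and/or treatment variables | 7.3.2 |
| Time cut-off for predictors | None stated | – |

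The first row is earlier than the end of the second. The third makes that true of every derivation record, and the fourth lets the later entries in.

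**4. Does anything in the plan filter on time?**

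- Section 7.3.1 removes the ED variables once the outcome is built. That closes the most direct leak but leaves the ambulance fields untouched.
- Penalisation (7.3.2) drops variables with little effect on the outcome. It does not look at timing and would tend to keep a late field that is informative.
- Bootstrapping and cross-validation (7.3.1, 7.4.3) resample the same cohort 1 records. They correct for overfitting, but a late value is just as late in each resample.
- Cohort 2 has no outcome (7.4.2), so a shift in predicted risk there could be seen but not judged right or wrong.

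**5. Effect of a restricted set on sample size.** Section 7.2 uses 520 parameters: 520 × 10 = 5,200 events, and 5,200/0.09 = 57,778. At 50 events per parameter, 520 × 50/0.09 = 288,889. Both figures reproduce. The protocol does not split the 520 by variable. Assuming, for illustration only, an even spread of 520/23 = 22.6 per variable:

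| Predictors kept | Parameters | Patients at 50 events per parameter, before inflation |
|---|---|---|
| 23 | 520 | 288,889 |
| 21 | 520 × 21/23 = 475 | 263,768 |
| 15 | 520 × 15/23 = 339 | 188,406 |

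The requirement falls or stays the same. It does not rise.

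**The case against.** A reader might infer that the eight items are recorded after the decision, that the model therefore does use information unavailable on scene, and that reported performance is inflated. The documents do not support this. Section 8.1 gives the span of the record, not the time of each entry. A second NEWS, airway care, drugs, cannulation or resuscitation may all come before the decision to convey, and patients advice is at least as plausible for someone discharged on scene. Inflation would further require that late entries are common and add prediction beyond the on-scene fields, and neither is shown.

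It can also be said that Table 1 is only an example, that the all-variables rule is for initial development, and that the final data specification (8.2.1), the objective of feasibility in practice (3.2.1) and the expert panel (7.4.4) each give an opportunity to drop an unusable field. For cohort 2, section 7.4.2 plans a frequency analysis that would reveal empty fields, and that cohort serves as a sense check rather than a source of accuracy estimates.

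The point about entry times stands: 8 of 23 is a ceiling, and the consequences are conditional. The later opportunities are real, but none is a rule about timing. Nor is this mere detail left to an analysis plan, because the protocol states an inclusive rule that does not fit its own stated use. A frequency table would show that a field is empty in cohort 2, but it would not show that a filled field in cohort 1 was filled too late.

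**Conclusion.** The concern holds in conditional form. The protocol fixes no prediction time, enters all assessment and treatment variables from a record that closes at handover, and intends the tool for use before transport. Up to 8 of the 23 example predictors can hold values recorded after the transport decision or resulting from it.

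If they do, apparent and bootstrap-corrected performance may overstate performance on scene, and these fields may be absent or differently distributed in cohort 2. The size of either effect cannot be worked out from the protocol. It depends on how often the fields are completed after the decision and how much they add to prediction.

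The mismatch itself rests on no numerical assumption. It follows from sections 1, 6.1, 7.3.2, 8.1 and 11.1.1 read together.

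**What to change.** In section 7.3.2:

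- Define the prediction time as the on-scene transport decision.
- In the main models, use only values recorded before departure from scene.
- Where a field has no usable time stamp, keep it only with a stated justification that it is known on scene before the decision. Dropping every such field outright would go further than the evidence warrants and could discard valid on-scene information.
- Report models with and without the doubtful items as a sensitivity analysis, and label any all-fields model as not usable on scene.

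In the data specification (section 8.2.1), request entry times for the fields concerned and the scene-departure time. This should be settled before retrieval: section 10.5.3 limits the request to potential predictors and linkage items, so times not asked for may not be supplied. The protocol does not say whether entry times are available for each field, which is why the justification route is needed.

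The cost is a short rule and some extra fields in the extract. Reported discrimination may be lower, and some on-scene treatment information may be lost. The required sample size does not rise, because there are fewer parameters.
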